5.3.3. Exploratory Efficacy Endpoints

Exploratory endpoints will be summarized by descriptive statistics. For comparison between inclacumab and placebo groups, point estimates, CIs, and p-values may be presented as appropriate, without adjustment for multiplicity.

Time to second VOC that required admission to a healthcare facility and treatment with parenteral pain medication within 90 days will be measured from randomization (Day 1) to onset date of the second protocol-defined VOC event and summarized using the same methodology as for time to first VOC (secondary endpoint).

The rate of complicated VOCs, rate of inpatient hospital admissions, and number of days of inpatient hospitalization for any reason during the 90 days following randomization will be summarized descriptively, using similar patient-time methodology as the rate of VOCs leading to a healthcare visit (secondary endpoint).

The proportion of participants rated as "very much improved" or "much improved" based on the PGI-C at Day 46 and Day 91 will be summarized descriptively by timepoint and treatment group. A similar analysis will be performed for the proportion of participants rated as "very much improved" or "much improved" based on the CGI-C.

A cumulative score for the ASCQ-Me Pain Impact (Short Form) will be calculated for each participant and assessment timepoint. For each assessment a cumulative score will only be calculated if all five questions on the form were answered. The cumulative score is the sum of the individual raw scores according to the response mapping in Table 3.

Table 3: ASCQ-Me Pain Impact (Short Form) Response Mapping

Response to Each Question	Raw Score
Always	1
Often	2
Sometimes	3
Rarely	4
Never	5

Changes from baseline over time to Day 91 will be calculated and summarized descriptively by timepoint (weekly) and treatment group.

5.4. Safety Analyses

Safety analyses will be based on the safety patient population (Section 4.2), with participants grouped according to the actual study treatment received. Safety will be assessed through descriptive summaries of adverse events, clinical laboratory test results, and vital signs.

5.4.1. Exposure to Study Drug and Compliance

Exposure to study drug (amount of study drug administered) will be summarized by treatment group.

For Day 1, the actual dose administered (in mg) and the difference between the planned dose and actual dose administered (in mg/kg) will be summarized descriptively by treatment group. For each participant, the percent compliance with study drug will be calculated based on the ratio of the actual dose administered (mg/kg) and the planned dose (i.e., 30 mg/kg). The percent compliance will be summarized by treatment group.

In addition, the number and percentage of participants with an infusion interruption will be summarized by treatment group.

5.4.2. Adverse Events

Adverse events will be classified according to MedDRA; the most current version at the time of analysis will be used. Severity of adverse events will be graded using the National Cancer Institute Common Terminology Criteria for Adverse Events (NCI CTCAE) version 5.0, when possible, or based on the protocol-specified grading for adverse events not covered in the NCI CTCAE.

Summaries of treatment emergent adverse events (TEAEs), defined as adverse events that occur on or after Day 1 of study treatment or the worsening of a preexisting condition on or after Day 1 of study treatment, will be tabulated by system organ class (SOC) and preferred term, as appropriate.

Summaries of TEAEs by treatment group will be provided for the following categories:

- All TEAEs
- All TEAEs by maximum severity
- TEAEs assessed as related to study drug by the investigator
- TEAEs leading to study drug interruption
- TEAEs leading to study drug discontinuation
- Adverse events of special interest (AESIs) (i.e., infusion-related reaction TEAEs)
- Treatment-emergent serious adverse events (SAEs)

Listings for all adverse events, TEAEs leading to study drug discontinuation, AESIs, SAEs, and deaths (if any) will be provided.

VOC events will be collected and summarized separately (uncomplicated VOC, acute chest syndrome [ACS], hepatic sequestration, splenic sequestration, and priapism).

5.4.3. Clinical Laboratory Assessments

Laboratory abnormalities assessed by the Investigator as clinically significant will be recorded as adverse events.

Descriptive summaries of laboratory parameters (hematology, serum chemistry, and coagulation) at baseline and each evaluation post baseline, as well as changes from baseline over time, will be provided by treatment group. If any of the results are below the limit of quantitation or above the limit of quantitation, then the numerical limit will be used in the descriptive summaries.

Laboratory abnormalities will be graded via the Common Terminology Criteria for Adverse Event (CTCAE). A treatment-emergent laboratory abnormality is any post-baseline laboratory assessment performed on or after initiation of study drug which demonstrates an increase of 1 grade or more from the baseline toxicity value. If the baseline value is missing, any graded abnormality (grade 1 or higher) that occurs following initiation of study drug will be deemed treatment emergent. The number and percentage of participants experiencing treatment-emergent laboratory abnormalities will be summarized by treatment group. Laboratory abnormality shifts from baseline through each evaluation post baseline will be summarized by treatment group.

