5.6. Unscheduled Visits for a VOC

Participants that visit a medical facility for treatment of a VOC will have blood samples obtained for complete blood counts (CBC), chemistry, coagulation, PK/PD, and biomarkers as outlined in Appendix 1, Appendix 2, and Appendix 3. Instructions for collection, preparation, and shipping of samples are provided in the Laboratory Manual.

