5.7. Additional Unscheduled Visits

Additional visits may be scheduled, as necessary, to ensure the safety and well-being of participants. All additional exams should be fully documented in the source documents and on Unscheduled Visit eCRFs, as appropriate. Visits intended to fulfill scheduled visit requirements that fall outside the designated scheduled visit range are not Unscheduled Visits. In these cases, the visit data will be collected and transcribed to the appropriate scheduled visit eCRF.

If a participant is seen for multiple visits during a given visit window, the data from the visit that is intended to meet the protocol requirements for the scheduled visit should be captured on the visit eCRF. Where such a determination cannot be made, the first visit within the scheduled visit interval will be used for completion of the protocol-required scheduled visit eCRF. Data from any additional visits within a scheduled visit interval will be captured on an Unscheduled Visit eCRF.

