2.2.4. Safety Endpoints

The safety endpoints for the study are the following:

- Incidence of treatment-emergent adverse events (TEAEs).
- Change from Baseline in laboratory assessments (complete blood count, chemistry, and coagulation).

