3.2. Visit Windows

For summaries by timepoint (e.g., CGI-C, PGI-C, vital signs, laboratory values), analysis visit windows will be used to classify assessments based on the actual study day of the measurement regardless of the original nominal visit label. This includes assessments collected at Unscheduled, Early Termination, or EOS visits. Target study days, the protocol-specified study day windows, and the analysis visit windows are shown in Table 1.

Table 1: Analysis Windows for Assessments Other than ASCQ-Me

Study Visit	Target Study Day	Visit Window per Protocol (study days)	Window for Statistical Analysis (study days)
Screening	-	[-10, -1]	[-10, -1]
Day 1	1	1	1
Day 46	46	[39, 53]	[32, 60]
Day 91	91	[84, 98]	[77, 105]
Day 161	161	[147, 175]	[140, 182]

ASCQ-Me=Adult Sickle Cell Quality of Life Measurement,

Note: Baseline is defined as the last available pre-treatment value taken on or before the day of randomization. Note: If multiple measurements fall within the statistical analysis window, the measurement closest to the target study day will be used. If two measurements are equally close, the earlier value will be used.

For the ASCQ-Me questionnaire (completed weekly at home), the analysis windows shown in Table 2 will apply for data summary.

Table 2: Analysis Windows for Assessment of ASCQ-Me

Analysis Timepoint	Target Study Day	Window for Statistical Analysis (study days)
Baseline	1	1
Week 1	8	[2, 11]
Week 2	15	[12, 18]
Week 3	22	[19, 25]
Week 4	29	[26, 32]
Week 5	36	[33, 39]
Week 6	43	[40, 46]
Week 7	50	[47, 53]
Week 8	57	[54, 60]
Week 9	64	[61, 67]
Week 10	71	[68, 74]
Week 11	78	[75, 81]
Week 12	85	[82, 88]
Week 13	92	[89, 95]

ASCQ-Me=Adult Sickle Cell Quality of Life Measurement

Note: Baseline is defined as the assessment taken on the day of randomization. If multiple measurements fall within the statistical analysis window, the measurement closest to the target study day will be used. If two measurements are equally close, the earlier value will be used.

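### Laboratory results drawn at a VOC presentation are pooled with scheduled ones, so the laboratory safety summaries depend partly on each arm's VOC rate

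*SAP*

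**What the plan says.** **Where the extra draws come from.** Protocol 5.6 states: "Participants that visit a medical facility for treatment of a VOC will have blood samples obtained for complete blood counts (CBC), chemistry, coagulation", with PK/PD and biomarker samples, as outlined in the appendices. The schedule in Protocol Appendix 1 marks CBC/chemistry and coagulation in the column for presentation with a VOC. A footnote ties sampling to the primary-endpoint definition of a VOC and to feasibility. These are the panels named in the laboratory safety endpoint of SAP 2.2.4: "Change from Baseline in laboratory assessments (complete blood count, chemistry, and coagulation").

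**How they are counted.** SAP 5.4.3 counts any qualifying post-baseline draw: "A treatment-emergent laboratory abnormality is any post-baseline laboratory assessment performed on or after initiation of study drug which demonstrates an increase of 1 grade"; larger rises count too, and the comparison is with baseline. The result is reported per participant: "The number and percentage of participants experiencing treatment-emergent laboratory abnormalities will be summarized by treatment group".

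**How they enter the by-visit summaries.** SAP 3.2 names laboratory values among the summaries that use analysis windows. The windows "classify assessments based on the actual study day of the measurement regardless of the original nominal visit label", and unscheduled visits are expressly included. The note to Table 1 adds: "If multiple measurements fall within the statistical analysis window, the measurement closest to the target study day will be used". The windows are Days 32 to 60 for Day 46 and Days 77 to 105 for Day 91.

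**What is kept apart.** SAP 5.4.2 summarizes VOC events separately from adverse events. No matching rule covers laboratory results drawn during those events.

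**The concern.** The treatment-emergent count records whether a participant ever shows a grade rise. Every further draw is another chance to be counted, and VOC draws are taken in acute illness. The protocol makes an acute fall in hemoglobin part of the definitions of hepatic and splenic sequestration (Section 5.1). The number of such draws depends on the efficacy outcome.

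If inclacumab works, placebo participants are sampled more often when sick, and the placebo column of the laboratory table rises with no direct drug effect on laboratory values. Part of that gap would be a genuine consequence of fewer VOCs. One pooled table cannot separate that part from a direct effect. In a safety table this is the unfavorable direction, because it can offset a modest direct laboratory harm in the inclacumab arm.

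The change-from-baseline summaries are touched only when a VOC draw lies nearer the target day than the scheduled draw, or fills an empty window. For example, a VOC draw on Day 45 would replace a scheduled draw on Day 52.

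**Working it through.** The documents state no figure for the laboratory summaries, so there is none to reproduce. The illustration borrows the design proportions, and the design calculation that uses them does reproduce. With 133 per arm (140 less 5% drop-out) and an O'Brien-Fleming-type Lan-DeMets boundary at information 75/140, power is 89.9% to 91.0%, against about 90% stated.

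**Inputs from the documents**
- Proportion with an admitted VOC in 90 days: 35% placebo, 17.5% inclacumab (SAP 2.3).
- Participants per arm: 0.26 × 280 / 2 = 36.4 (SAP 2.3, 1:1 allocation).

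**Assumptions**
- Admitted VOCs are Poisson: −ln(0.65) = 0.431 per placebo participant and −ln(0.825) = 0.192 per inclacumab participant.
- One sampled presentation per admitted VOC.
- s, the chance of a treatment-emergent abnormality at scheduled draws, is the same in both arms, 10% to 95%.
- q, the chance that a VOC is sampled and shows a grade rise, is 0.1 to 0.5, independent of the scheduled results.
- No direct drug effect on laboratory values.

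**Treatment-emergent count.** P(any abnormality) = 1 − (1 − s) × exp(−rate × q).

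| s | q | Placebo | Inclacumab | Gap (points) | Standard error (points) |
|---|---|---|---|---|---|
| 10% | 0.5 | 27.4% | 18.3% | 9.2 | 9.8 |
| 20% | 0.3 | 29.7% | 24.5% | 5.2 | 10.4 |
| 50% | 0.3 | 56.1% | 52.8% | 3.3 | 11.7 |
| 80% | 0.3 | 82.4% | 81.1% | 1.3 | 9.0 |
| 95% | 0.5 | 96.0% | 95.5% | 0.5 | 4.7 |
| 95% | 0.1 | 95.2% | 95.1% | 0.1 | 5.0 |

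The standard error is √[(P₁(1 − P₁) + P₂(1 − P₂)) / 36.4]. At s = 20% and q = 0.3 the gap is 36.4 × 0.052 = 1.9 participants. If the VOC rate, rather than the proportion, is halved, the gap there is 4.7 points.

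**Cross-check with at most one VOC draw per participant.** The gap is (1 − s) × q × (0.35 − 0.175). At s = 20% and q = 0.3 this is 0.8 × 0.3 × 0.175 = 4.2 points. In this simpler model the placebo figure is 0.20 + 0.80 × 0.35 × 0.3 = 28.4%. A true inclacumab excess at scheduled draws of (0.284 − 0.0525) / (1 − 0.0525) − 0.20 = 4.4 points would bring the two arms level, where 0.0525 = 0.175 × 0.3.

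**Window displacement.** Take the scheduled visit as uniform over the 15 days within 7 days of target, and the VOC day as uniform over Days 1 to 91. The nearer value wins, and ties go to the earlier.
- Day 46: 105 of 15 × 91 = 1,365 combinations favor the VOC draw, or 7.7%. Participants displaced: 36.4 × 0.431 × 0.077 = 1.2 placebo, 36.4 × 0.192 × 0.077 = 0.5 inclacumab.
- Day 91: 63 of 1,365, or 4.6%. Participants displaced: 0.7 placebo, 0.3 inclacumab.

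Re-admissions cluster early. Protocol 1.2 gives about one third by 30 days and about 50% by 90, so about 66% of 90-day events fall in the first 30 days. SAP 2.3.1 gives 26.9% × 86% = 23% by 30 days, which against 50% is 46%. These figures count from hospitalization, so they are only approximate from randomization. Both windows start after Day 30. With 46% to 66% of events before Day 31 and the rest uniform to Day 91, displacement falls to 0.6–1.0 placebo versus 0.3–0.4 inclacumab at Day 46, and 0.4–0.6 versus 0.2–0.3 at Day 91.

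**The case against.** **The rule is deliberate.** Counting every post-baseline draw is an inclusive safety convention. SAP 3.2 includes unscheduled visits on purpose, and the SAP takes precedence over the protocol where they differ. Safety is descriptive and efficacy is untouched. Fewer VOC-related abnormalities on inclacumab is itself part of the randomized effect. All of this stands, and it is why the point is an improvement and not an error.

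**The inputs may be generous.** A summary pooled over all analytes could have s above 80%, which nearly removes the gap. Baseline is taken within about 5 days of index VOC resolution, so baseline grades may still be raised and leave less room for a further rise. Sampling is only if feasible. Abnormalities may recur in the same participants. Each of these lowers the estimate.

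**The split may exist elsewhere.** Table mock-ups are in a separate document and might divide the draws, but the SAP text does not require it. Abnormalities judged clinically significant are also recorded and listed as adverse events.

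**Two stronger readings are tempting.**
- A reader might infer that the SAP reverses Protocol 5.7, which says that "the data from the visit that is intended to meet the protocol requirements for the scheduled visit should be captured on the visit eCRF" and "Data from any additional visits within a scheduled visit interval will be captured on an Unscheduled Visit eCRF". That section governs eCRF entry for additional visits. VOC visits have their own Section 5.6, which names no eCRF for their laboratory results. It is not an analysis rule that the SAP contradicts.
- A reader might infer several sampled visits per admitted VOC, and so a much larger gap, because the synopsis extends sampling to VOCs without re-admission. No document gives a count, and Section 5.6 defers to Appendix 1, whose footnote restricts sampling to the primary-endpoint definition.

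**Conclusion.** The concern holds as a modest, inexpensive improvement. As written, the treatment-emergent laboratory count depends partly on each arm's VOC rate, and the by-visit change-from-baseline summaries do so to a small extent. If inclacumab reduces VOCs, the dependence favors inclacumab and could mask a modest adverse laboratory signal.

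Across the assumed range the placebo excess is about 0.1 to 9 points, less than its standard error in every case tried. The upper end needs a low background rate and a high chance that a VOC draw shows a grade rise. Displacement, over both timing assumptions, is 0.6–1.2 placebo versus 0.3–0.5 inclacumab participants at Day 46, and 0.4–0.7 versus 0.2–0.3 at Day 91. If VOC rates are equal, the systematic gap is zero.

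The size rests on s, q and one sampled presentation per admitted VOC, none of which the documents supply. It covers the first 90 days only. Nothing here supports a claim that the laboratory tables are wrong or that efficacy results are affected.

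**What to change.** **SAP 3.2, add:** *For laboratory parameters, a result drawn at presentation for a VOC will be used only if no other result is available in that analysis window.* Other unscheduled visits and retests keep the closest-to-target rule, so a repeat test or a better-timed unscheduled draw is not displaced by this change.

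**SAP 5.4.3:** keep the all-draws treatment-emergent table as the main table, so that an abnormality first seen at a VOC still counts. Add one companion table (n, %) that excludes VOC-presentation draws, and report the number of post-baseline draws per participant by arm.

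**Cost:** one flag, one extra descriptive table and no new data. If no eCRF field identifies these draws, the flag can be derived by comparing draw dates with recorded VOC dates. The two tables must be read together: the companion removes the dependence on VOC draws but also omits any drug-related abnormality seen only at a VOC.

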5.4.4. Vital Signs and Weight

[figure not shown]
Descriptive summaries of vital signs (e.g., systolic and diastolic blood pressure, heart rate, and body temperature) at baseline and each evaluation post baseline, as well as changes from baseline over time, will be generated by treatment group. In addition, descriptive summaries of weight at baseline will be generated by treatment group.

5.5. Exploratory PK, ADA, and PD Analyses

5.5.1. Pharmacokinetic Analyses

[figure not shown]

5.5.2. Anti-drug Antibody Analyses

CCI

5.5.3. Pharmacodynamic Analyses

6. TABLES, LISTINGS, AND FIGURES

A separate document will provide mockups of the tables, listings, and figures that support the analyses proposed in this SAP.

